4.8 OTHER ANALYSES

4.8.1 Pharmacokinetic analysis

Plasma BIVV009 concentrations will be listed by subject, nominal visit, date and time of collection and study day. Summary statistics of plasma BIVV009 concentrations will be presented by nominal visit and study day including n, mean, standard deviation, coefficient of variation, geometric mean, median and range. All summaries will be tabulated by treatment cohort in Part B (ie, 6.5 g and 7.5 g) and Total. Individual and mean plasma BIVV009 concentration-versus-time profiles will be plotted. The above analyses will be conducted using the PK Analysis Set for the Cumulative Study Period.

4.8.2 Pharmacodynamic analysis

Descriptive statistics including number of observations, mean, SD, median, minimum, and maximum will be presented for continuous parameters. Categorical variables will be presented with the number and percentage in each category. Summary descriptive statistics (absolute values and changes from baseline) and individual subject listings will be presented by time point and study day. All summaries will be tabulated by treatment cohort in Part A (ie, BIVV009 and Placebo) and Total. The above analyses will be conducted using the PD Analysis Set for the Cumulative Study Period.

4.9 INTERIM ANALYSES

For purposes of regulatory submission, an interim analysis of safety and efficacy data will be performed after all subjects have completed Part A and the data are cleaned. Part B data, up to the date of Part A database lock, will be summarized descriptively.

5 SUPPORTING DOCUMENTATION

5.1 APPENDIX 1 LIST OF ABBREVIATIONS

AE	adverse event
ADL	activities to daily living
ALP	alkaline phosphatase
ALT	alanine aminotransferase
ANA	antinuclear antibodies
AST	aspartate aminotransferase
AUC	area under the curve
BLA	Biologics License Applications
BUN	blood urea nitrogen
CAD	cold agglutinin disease
CI	confidence interval
CIC	circulating immune complexes
C _{max}	maximum concentration
CTCAE	Common Toxicity Criteria for Adverse Events
DBL	database lock
ECG	electrocardiogram
eCRF	electronic Case Report Form
EOT	end of treatment
EQ-5D-5L	EuroQol – five dimensions questionnaire
ET	early termination
FACIT	functional assessment of chronic illness therapy
FAS	full analysis set
GGT	gamma-glutamyl transferase
Hgb	hemoglobin
HUI	health utility index
ICH	International Conference of Harmonisation
ITT	intent-to-treat
IV	intravenous
LDH	lactate dehydrogenase
LLN	lower limit of normal
LPO	last patient out
MAA	Marketing Authorization Application
MAR	missing at random
MCMC	Markov chain Monte-Carlo
MedDRA	Medical Dictionary for Regulatory Activities
MMRM	Mixed Model for Repeated Measures
MNAR	Missing Not At Random
NCMV	Neighboring-Case Missing Value
PD	pharmacodynamics
PGIC	Patient's Global Impression of Change
PGIS	Patient's Global Impression of Severity

PK	pharmacokinetics
PP	per-protocol
PRO	patient-reported outcome
QOL	quality of life
RBC	red blood cell count
SAE	serious adverse event
SAP	Statistical Analysis Plan
SD	standard deviation
SF-12	12-Item Short Form Survey
SGOT	serum glutamic oxaloacetic transaminase
SGPT	serum glutamic-pyruvate transaminase
SLE	systemic lupus erythematosus
SOC	system organ class
TEAE	treatment-emergent adverse event
TLF	tables, figures, and listings
TOEPH	heterogeneous Toeplitz
ULN	upper limit of normal
WBC	white blood cell count

5.2 APPENDIX 2 CHANGES TO PROTOCOL-PLANNED ANALYSES

This section summarizes major statistical changes in the protocol amendment(s).

Table 7 - Major statistical changes in protocol amendment(s)

Amendment Number	Approval Date	Changes	Rationale
Version 1 (original)	24-Aug-2017	Not applicable	Not applicable

5.3 APPENDIX 3 DEMOGRAPHICS AND BASELINE CHARACTERISTICS, PRIOR OR CONCOMITANT MEDICATIONS

Demographics and baseline disease characteristics will be summarized for the FAS.

Demography

Demographic characteristics including age (years), age category (<65, >= 65), gender, race, ethnicity, country, geographic location, height (cm), weight (kg), weight category (<75 kg, >= 75 kg), and body mass index (kg/m²) will be summarized. Geographic locations are defined as Europe, North America, Asia/Japan, and other.

General Medical History

Medical history by system organ class (SOC) and preferred term (PT) will be summarized. A subject will be counted only once if they reported one or more occurrences in the same SOC or PT.

A summary of prior hospitalizations related to CAD within the last 2 years, prior hematological malignancies within the last 5 years, prior non-malignant hematologic diseases within the last 5 years, and prior thromboembolic events within the last 1 year will be presented based off the “Targeted Medical History” eCRF form.

Baseline Disease Characteristics

Screening and baseline lab parameters, including hematology (such as Hgb, bilirubin, LDH), Gilbert’s Syndrome testing, and bone marrow biopsy results will be summarized. Prior transfusion history (eg, number of transfusions within 12 months of study entry) will also be summarized.

Severity of anemia symptoms and other CAD-related disease characteristics (eg, presence of acrocyanosis, Raynaud’s syndrome, hemoglobinuria, disabling circulatory symptoms, and major adverse vascular events) within 3 months of screening will be summarized.

The proportion of subjects who had documented vaccines within 5 years and who have received vaccination during the study will be summarized. The vaccines include meningococcal vaccine, S. pneumoniae vaccine, and H. influenza vaccine.

Prior or concomitant medications

Prior medications are those taken before the first dose of study drug in Part A. Concomitant medications are those administered on or after the first dose of study drug, or those administered before the first dose that are ongoing when study treatment begins. Prior and concomitant medications will be coded using World Health Organization drug enhanced dictionary (March 2020 version or higher).

Separate tables will be generated to summarize concomitant medications and concomitant protocol-prohibited medications by ATC level 2 and WHODrug standardized medication text.

Additionally, a summary of targeted prior therapies will be generated based off the responses provided in the “Targeted Prior Therapy” eCRF form.

Concomitant non-drug treatments and procedures

Concomitant non-drug treatments and procedures will be summarized for the FAS.

5.4 APPENDIX 4 DATA HANDLING CONVENTIONS

Study Day

Study Day is defined as days relative to the date of first dose of BIVV009 or placebo in Part A, Day 0. The start/stop day of events will be calculated as (date of event – date of Day 0 +1).

Incomplete dates will be imputed for the calculation of study days, unless specified otherwise:

- If missing day only, the start date will be imputed as the first day of the month, while the end date will be imputed as the last day of the month;
- If missing day and month, the start date will be imputed as the first day of the year, while the end date will be imputed as the last day of the year;

Baseline

For purposes of specified analyses, baseline measures are defined as the last value prior to the first dose of study drug in Part A.

Analysis Windows for time points

Analysis by study visit will utilize the data recorded on the corresponding nominal visit from electronic Case Report Forms (eCRFs). In case of missing data/assessments for a visit, data from an unscheduled visit, or ET/Safety Follow-up Visit will be used, if the Study Day of such a visit fits in the analytic window defined below. If multiple values are identified within the analytic window, the one closest to the target study day will be used.

Starting at Week 27 and every 2 weeks thereafter, analytic visit windows in Part B will be -6 days to +7 days from the Target Study Days of the protocol-defined visits. An example of the first few visits in Part B can be seen below .

Table 8 - Analytic visit window

Visit	Target Study Day	Analytic Visit Window (Study Day)
Week 27	189	183-196
Week 29	203	197-210
Week 31	217	211-224
Week 33	231	225-238
Etc.		

Unscheduled visits

Unscheduled visit measurements of clinical laboratory data, ECG and vital signs will be used for computation of baseline, the last on-treatment value, analysis according to PCSAs, and the shift summaries for safety. They will also be included in the by-visit summaries if they are re-allocated to scheduled visits.

Pooling Sites for Analysis

Data from all investigational sites will be pooled for the analysis, unless specified otherwise.

Handling of Missing Data

Best efforts will be utilized to minimize missing values. If a subject discontinues study treatment early, the subject will be asked to complete study assessments at ET/safety follow up visit.

For the analysis of both continuous and categorical data, summary statistics will be computed based on observed data. Since the duration of treatment period varies in Part B, efficacy endpoints by visit will be summarized through 12 months during Part B. Additional summaries beyond 12 months may be computed depending on the enrollment pattern, ie, the number of subjects attending visits after the Week 77 visit. AE endpoints by visit will be summarized through LPLV in Part B.

For a QOL endpoint, in the event of missing data, the total score will be estimated according to the provision for missing domains in the calculation algorithm of the score. For example, if a subject has missing data in FACIT-F questionnaire at a visit, the prorated FACIT-F score will be calculated if more than 50% of the items (a minimum of 7 out of 13 items) are available. Otherwise, the score is missing.

For the analysis of AEs and concomitant medications/procedures, if the start/stop date of an AE/concomitant medication/procedure is missing or partial, the corresponding study day will be left blank. However, inferences will be made from the partial and missing dates to classify modifications as prior and/or concomitant and AEs as treatment emergent or not treatment emergent.

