4.7.1 Extent of exposure

The extent of IMP exposure will be assessed by the duration of IMP exposure and treatment compliance and summarized for the Safety Analysis Set. Per the protocol, all subjects rolling over to Part B are to receive a loading dose (in a blinded manner). For analysis of Part A exposure, this loading dose will not be included in the Part A database. Thus, Part A exposure will end 1 minute prior to the date/time of the Week 26 loading dose, and Part B exposure will start on the date/time of the Week 26 loading dose.

Duration of IMP exposure

Study drug exposure, measured by the duration of study treatment, number of administrations, and total actual BIVV009 dose will be summarized for the Safety Analysis Set.

The duration of the study treatment (in weeks) in Part A is defined as:

- $(\text{Date of Week 26 visit} - \text{Date of first dose} + 1)/7$, if a subject enrolls into Part B;
- $(\text{Date of last dose} - \text{Date of first dose} + 15)/7$, if a subject discontinues study treatment early in Part A or does not enroll into Part B.

Treatment compliance

Study drug compliance for a subject is measured by the percent of number of doses received out of the number of protocol-specified doses. For example, for a subject who completes Part A treatment, the number of protocol-specified doses is 14. The compliance of the subject will be the

number of doses received divided by 14 expressed in percentage. For a subject who discontinues early in Part A, the number of protocol specified doses is the number of scheduled doses prior to the date of discontinuation. The proportion of subjects whose compliance is less than 80%, 80% – <100%, and $\geq 100\%$ will also be summarized. In addition, the number of subjects and number of doses administered out of study windows and number of partial infusion doses will also be summarized.

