5.4 APPENDIX 4 DATA HANDLING CONVENTIONS

Study Day

Study Day is defined as days relative to the date of first dose of study drug (BIVV009 or placebo) in Part A (Day 0 as in the protocol). The Study Day of an event is calculated as

- (date of event – date of first dose of study drug in Part A + 1), if the event is on or after the first dose date;
- (date of event – date of first dose of study drug in Part A), if the event is prior to the first dose date.

The date of the first dose of study drug in Part A is Study Day 1.

Baseline

Baseline measures are defined as the last value prior to the first dose of study drug. If a subject receives a transfusion during the screening period, the baseline measure must be at least 7 days after the transfusion.

Visit Windows

Analysis by study visit will utilize the data recorded on the corresponding nominal visit from electronic Case Report Forms (eCRFs). In case of missing data/assessments for a visit, data from an unscheduled visit, or ET/Safety Follow-up Visit will be used, if the Study Day of such a visit fits in the analytic window defined in [Table 14](#), below. If multiple values are identified within the analytic window, the one closest to the target study day will be used.

[figure not shown]
Table 14 - Analyses window definition

[figure not shown]
Visit	Target Study Day	Analytic Visit Window
Baseline (Day 0)	1	≤1
Week 1 (Day 7)	8	2 – 15
Week 3 (Day 21)	22	16 – 29
Week 5 (Day 35)	36	30 – 43
Week 7 (Day 49)	50	44 – 57
Week 9 (Day 63)	64	58 – 71
Week 11 (Day 77)	78	72 – 85
Week 13 (Day 91)	92	86 – 99
Week 15 (Day 105)	106	100 – 113
Week 17 (Day 119)	120	114 – 127
Week 19 (Day 133)	134	128 – 141
Week 21 (Day 147)	148	142 – 155
Week 23 (Day 161)	162	156 – 169
Week 26 (Day 175)	176	170 – 179
Week 26 (Day 182; EOT Visit in Part A)	183	180 – 189

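### The Part A Week 26 window has no pre-crossover limit, so in rare cases a placebo patient's post-BIVV009 Hgb could enter the primary endpoint mean; separately, the Part B window table is one day short and overlaps Part A

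*SAP*

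**What the plan says.** **Part A SAP, Section 5.4.** Study Day is "date of event – date of first dose of study drug in Part A + 1), if the event is on or after the first dose date", and "The date of the first dose of study drug in Part A is Study Day 1". Analyses use the nominal visit value. If it is missing, a value from an unscheduled or ET/Safety Follow-up visit is used when its Study Day falls in the Table 14 window. The last row reads "Week 26 (Day 182; EOT Visit in Part A) 183 180 – 189". The row above it is labelled "Week 26 (Day 175"), with target 176 and window 170-179. There is no Week 25 row.

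**Where these values go.** Part A SAP Section 4.1 defines the treatment assessment value as the average of the available Week 23, 25 and 26 values. The primary responder rule tests it against a 1.5 g/dL rise. Protocol Section 7.3.2 leaves assignment to analysis visits to the SAP windows.

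**Crossover.** Protocol Section 6.1.4 places the crossover loading dose at the Week 26 visit, once the end-of-treatment assessments are done. Under Protocol Section 4.1, former placebo patients then receive BIVV009 and former BIVV009 patients receive placebo. For exposure only, Part A SAP Section 4.7.1 draws the line exactly: "Part A exposure will end 1 minute prior to the date/time of the Week 26 loading dose".

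**Part B SAP, Section 5.4.** The same numbering applies: "The start/stop day of events will be calculated as (date of event – date of Day 0 +1"). The window rule is "analytic visit windows in Part B will be -6 days to +7 days from the Target Study Days". Table 8 lists Weeks 27, 29, 31 and 33 at targets 189, 203, 217 and 231, with Week 27 covering 183-196. The fallback to unscheduled or ET/Safety Follow-up values matches Part A.

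**The concern.** The Part A Week 26 window extends beyond the visit at which the placebo arm stops being a placebo arm. The exposure section recognises that boundary to the minute, but the window rule does not mention it. Read literally, the rule can bring an on-drug Hgb into the placebo arm's treatment assessment mean, and so into the primary responder classification and the Week 26 term of the key secondary Hgb model.

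The Part B table raises a different and lesser issue. It contradicts the formula printed just above it. Its first window also covers days already allotted to Part A, and neither SAP says which part owns an unscheduled value in the shared days. The consequence falls on the descriptive by-visit summaries.

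**Working it through.** **1. Part A targets, to confirm the convention.** Study Day = protocol day + 1.
- Week 25: 175 + 1 = 176, as printed.
- Week 26: 182 + 1 = 183, as printed.

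All the other Table 14 post-baseline targets also reproduce. The Day 175 row therefore has the right numbers under the wrong week label, since 175 / 7 = 25.

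**2. Post-dose days inside the Part A Week 26 window.** The window ends at Study Day 189. Protocol Table 3 allows the Week 26 visit at Day 182 ± 2.

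| Dose on protocol day | Study Day | Window days after dose |
|---|---|---|
| 180 | 181 | 189 - 181 = 8 |
| 182 (nominal) | 183 | 189 - 183 = 6 |
| 184 | 185 | 189 - 185 = 4 |

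**3. Which post-dose values can use the fallback.**
- A scheduled Week 27 draw (Day 189 ± 2, Study Days 188-192) can fall on Study Day 188 or 189, but it is neither an unscheduled nor an ET/Safety Follow-up visit.
- An ET/Safety Follow-up visit is due 9 weeks (63 days) after the last dose, ± 2 days. After the earliest in-window crossover it falls no sooner than 181 + 63 - 2 = 242, well past 189.
- That leaves an unscheduled draw taken after the dose and by Study Day 189, in a patient dosed at Week 26 whose Hgb from that visit is missing.

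**4. Weight of one such value.** It carries 1/3 of the mean if Weeks 23 and 25 are present, 1/2 if one of them is, and all of it if neither is. The documents give no figure for the Hgb rise within days of a first dose. Assuming 0.5 to 2 g/dL relative to a pre-dose value, the mean shifts by:

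| Values available | Rise 0.5 g/dL | Rise 2 g/dL |
|---|---|---|
| 3 | 0.5 / 3 = 0.17 | 2 / 3 = 0.67 |
| 2 | 0.5 / 2 = 0.25 | 2 / 2 = 1.0 |
| 1 | 0.5 | 2.0 |

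The responder threshold is 1.5 g/dL.

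**5. Part B Table 8.** Target = 7 × week + 1; window = target - 6 to target + 7.

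| Week | Printed target | Printed window | Target by formula | Window by formula |
|---|---|---|---|---|
| 27 | 189 | 183-196 | 190 | 184-197 |
| 29 | 203 | 197-210 | 204 | 198-211 |
| 31 | 217 | 211-224 | 218 | 212-225 |
| 33 | 231 | 225-238 | 232 | 226-239 |

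The printed windows follow from the printed targets, so the error lies in the targets alone. Each is one day short.

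**6. Overlap with Part A Week 26 (180-189).**
- As printed: 183-189, seven days.
- With the targets corrected: 184-189, six days. The post-dose days inside the Part A window do not change.

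Correcting Table 8 therefore does not resolve the overlap and has no bearing on step 2.

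**The case against.** The best defence is that the boundary is already set. Part A SAP Section 4.1 ends the Part A treatment period at the Week 26 visit date, Part B SAP Section 4.1 starts Part B immediately after that visit, and the exposure section cuts at the loading dose. A post-dose draw would then belong to Part B by definition. This shows the intent, but those definitions govern the treatment period and exposure. The fallback rule in Section 5.4 refers to neither, and a programmer applying Table 14 as written would accept the value.

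The defence is also right that the route is narrow. Nominal values come first, Hgb is on the scheduled Week 26 panel, and a patient whose Week 26 visit is late has not yet crossed over, so a late value can still be pre-dose. The BIVV009 arm receives placebo at crossover and has no equivalent problem. The documents identify no affected patient.

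Four stronger readings are tempting and are not supported:
- **That the Part B table contaminates the primary endpoint.** Part A has its own windows and its own database lock. Neither the one-day error nor the overlap feeds its endpoint.
- **That both key secondaries are exposed.** In Part B, FACIT-Fatigue is scheduled every 3 months (Protocol Table 3 and Section 6.1.5.3), so none is planned in the days just after Week 26. Only the Hgb endpoint is realistically affected.
- **That the flaw favours the drug.** If Hgb rises after BIVV009, the stray value raises the placebo arm.
- **That the one-day shift disturbs Part B materially.** Scheduled Week 27 visits (Study Days 188-192) lie inside both the printed and the corrected window, and Part B tests no hypotheses. Only an unscheduled value on a boundary day, replacing a missing visit, would move; Study Day 197, for example, now goes to Week 29 rather than Week 27.

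**Conclusion.** The point holds as a minor correction in two separate parts.

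- **Part A.** The Week 26 window admits unscheduled values for about 4 to 8 days after the crossover dose (6 at nominal timing). It matters only for a placebo patient dosed at Week 26, with that visit's Hgb missing and an unscheduled draw by Study Day 189. For that patient an on-drug Hgb would carry at least one third of the treatment assessment mean, and could alter responder status if the mean is near the threshold. The sizes in step 4 rest on an assumed rise. The expected direction, a smaller treatment difference, rests on Hgb rising on drug; Protocol Section 2.2.2 reports rapid correction of anemia but no figure for these few days.
- **Part B.** All four printed Table 8 targets are one day short, and the Week 27 window shares seven days with Part A Week 26. If both nominal values are missing, one unscheduled draw could fill both visits. Of the seven days, Study Day 183 is the nominal end-of-treatment day itself, when assessments precede the dose.

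The label "Week 26 (Day 175") is a slip, but it sits on a visit that the primary endpoint names as Week 25.

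**What to change.** **Part A SAP, Section 5.4**
- Add one sentence: a value may populate Week 26 only if it was collected before the Week 26 crossover dose, using the same dose date and time that already end Part A exposure. State a default for an unscheduled draw on the dosing date with no recorded time.
- Relabel the Day 175 row Week 25.

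**Part B SAP, Section 5.4, Table 8**
- Set the targets to 190, 204, 218 and 232, with windows 184-197, 198-211, 212-225 and 226-239, and carry the one-day correction through the later visits.
- Accept a value for Week 27 only if it was collected after the crossover dose. Both dose-based limits are needed, because the corrected windows still share Study Days 184-189 with Part A.

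The cost is two sentences and table edits across the two SAPs, with matching changes to the visit-assignment programs. No new data collection is planned, and the edits should be made before the Part A database lock.

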#### 3.4 SECONDARY OBJECTIVE (PART B)

The secondary objective of Part B is

- To investigate the durability of response during long-term treatment with BIVV009 in patients with primary CAgD
- To evaluate the immunogenicity of BIVV009

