## Part B

Following completion of dosing in the initial 6-month treatment period, patients will roll into the long-term safety and durability of response extension phase and receive BIVV009 in an open-label manner. Part B will run for 1 year following last patient out (LPO) under Part A. Patients requiring treatment with permitted concomitant medications and/or transfusions will not be discontinued from the study. Patients in Part B will be transfused per the transfusion criteria in [Table 1](#). Patients who receive a transfusion in Part B will not be withdrawn from the study.

Blinding will be maintained when rolling patients into the extension period by providing a crossover dose at Week 26 to allow placebo patients to receive the BIVV009 loading dose at start of BIVV009 dosing. Patients who were randomized to BIVV009 during the 6-month treatment period will receive a placebo dose at Week 26 to maintain blinding. All patients will then continue to receive bi-weekly BIVV009 dosing starting at Week 27.

Patients will be dosed with BIVV009 every 2 weeks, as in Part A. Should patients deviate from their scheduled dosing, a repeat loading dose may be required. On-site visits will be completed ~ every 3 months (at a minimum) for collection of PK, PD and ADA samples, and additional safety and efficacy measures.

Home infusion will be performed by a healthcare professional caregiver contingent upon completion of training delivered by the Investigator or delegated site staff member only in patients willing to be administered study drug in home, who have been treated with at least 3 months with BIVV009 in Part B and who satisfy the criteria mention in the appendix K ([Appendix K](#)).

A subset of patients from countries pre-selected to participate in home infusion, who have been treated for a minimum 3 months (completed visit Day 273) in Part B and who were determined

to have tolerated BIVV009 well, will be invited to have infusions with BIVV009 performed at their homes, after having been qualified by the Investigator. Home infusion will be performed by a healthcare professional caregiver contingent upon completion of training delivered by the Investigator or delegated site staff member. Patients will follow the alternate home infusion scheme, ie, home infusion at the patient's home will be alternating with office visits, so that patients will attend office visit every 4 weeks alternating with home infusions every 4 weeks ( $\pm 2$  days) ([Appendix K](#)).

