1.2 OBJECTIVE AND ENDPOINTS

Table 2 - Objectives and endpoints

	Objectives	Endpoints
Primary	
 The primary objective of Part B is to evaluate the long-term safety and tolerability of BIVV009 in patients with primary CAD 	
Safety Endpoints:
 
 Incidence of treatment-emergent adverse events (TEAEs) and serious adverse events (SAEs) Change from baseline in clinical laboratory evaluations Change from baseline in systemic lupus erythematosus (SLE) panel Change from baseline in vital signs Change from baseline in electrocardiograms (ECG) data Physical examination findings Incidence of infections of \geq Grade 3 severity (ie, requiring intravenous [IV] antibiotics) Serum disease-related biomarkers Incidence of hemolytic breakthrough through EOT Incidence of thromboembolic events
Secondary	
 The secondary objective of Part B is to investigate the durability of response during long-term treatment with BIVV009 in patients with primary CAD. 	
The following parameters of disease activity will be assessed:
 
 Hemoglobin Bilirubin QOL assessments (FACIT-Fatigue, EQ-5D-5L, SF-12, PGIS, and PGIC) LDH Transfusion requirements Haptoglobin Total healthcare resource utilization at EOT
Tertiary/exploratory	
 To describe the safety and patient satisfaction with the convenience of home infusions with BIVV009 in a subset of patients To describe the safety of undiluted infusions with BIVV009 To evaluate the immunogenicity of BIVV009 	
For subjects receiving home infusions:
 
 Satisfaction with home infusion after first home infusion and after fourth home infusion Incidence of AEs with onset within 24 hours of a home infusion 
For subjects receiving undiluted infusions:
 
 Incidence of AEs with onset within 24 hours of an undiluted infusion Anti-drug antibodies

Objectives	Endpoints

• Pharmacokinetics of BIVV009	
• Plasma concentrations of BIVV009• PK parameters: Appropriate exposure parameters (C_{max}, AUC) will be derived using a population PK approach

• Pharmacodynamics of BIVV009	
• Weislab-CP• CH50• Total C4• C1q• C1s

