1.2.1 Estimands

There are no primary efficacy endpoints in Part B. Thus, estimands will not be utilized in this SAP.

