4.4.1.2 Main analytical approach

Continuous Endpoints

The continuous endpoints will be summarized by visit and treatment arm using descriptive statistics for the FAS according to [Section 4.1](#). Change from baseline will also be summarized by visit.

Line plots of hemoglobin, bilirubin, and FACIT-F score over time, starting at Baseline/Day 0, will be presented. Additionally, line plots of mean change from baseline in hemoglobin, bilirubin, and FACIT-F score over time, starting at Baseline/Day 0, will be presented.

The endpoints related to transfusions and transfusion units will be summarized by study period using the FAS.

Annualized values will be calculated for each patient using the following formula:

$$\text{Annualized value} = \frac{\text{Number of events during the Study Period}}{\text{Total number of days during the Study Period}} \times 365.25$$

Response (Categorical) Endpoints

The categorical endpoints will be summarized descriptively by visit and treatment arm for the using the FAS according to [Section 4.1](#) with the exception of total healthcare resource utilization at EOT (Part A), which will be presented in a listing.

All thromboembolic events reported (in Adverse Events) will be reviewed and determined by internal medical staff along with investigators. In case that there are discrepancies between the medical review and investigators' assessment, separate analyses will be carried out for both sets of events. Date of event occurrences will be verified. The incidence of thromboembolic events and hemolytic breakthrough events will be summarized using all data in Part B (including data from the Week 79 visit and beyond).

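### Part B's secondary objective is durability of response, but no endpoint measures maintained or lost response, and the by-visit means have no rule for transfusion or stopping

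*SAP*

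**What the plan says.** Protocol 3.4 gives the objective: "To investigate the durability of response during long-term treatment with BIVV009 in patients with primary CAgD". Part B SAP 1.2 repeats it and lists disease-activity parameters against it: Hgb, bilirubin, LDH, haptoglobin, quality of life, transfusion requirements and resource use.

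Part B SAP 4.4.1.2 sets the method: "The continuous endpoints will be summarized by visit and treatment arm using descriptive statistics for the FAS". Part B SAP 1.2.1 declines to set a strategy for intercurrent events: "There are no primary efficacy endpoints in Part B. Thus, estimands will not be utilized in this SAP". Part B SAP 5.4 adds "For the analysis of both continuous and categorical data, summary statistics will be computed based on observed data", with by-visit efficacy summaries through 12 months of Part B.

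On transfusion, Protocol 4.1 (Part B) says "Patients who receive a transfusion in Part B will not be withdrawn from the study". On stopping, Part B SAP 5.4 lets an early-termination or safety follow-up value fill a missing visit when it falls in the analytic window. Part B SAP 4.1 places that visit 9 weeks after the last dose.

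Part B SAP 4.4.1.1 and 4.4.1.2 also plan the number and units of transfusions, annualized versions of both, and hemolytic breakthrough over all Part B data. Part B SAP 4.2 tabulates early discontinuation with its main reason.

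**The concern.** Durability concerns individual responders: of those who responded, how many kept the response, and for how long? A mean over whoever has a value at a visit does not answer that, even when it is unbiased.

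The mean may also lean upward, for two reasons that the protocol itself supplies. Transfusion is triggered by low Hgb (Protocol Table 1), so transfusion-raised values come from patients whose control has slipped, and those patients stay in the summaries. The withdrawal reasons in Protocol 5.3 include breakthrough hemolysis put down to anti-drug antibodies and the taking of non-permitted medication, so some stopping is tied to loss of response. Those patients leave the later means.

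The follow-up visit creates a separate problem. Its value is taken off drug, and Protocol 2.2.2 reports that hemolytic anemia returned on washout. Placed in a by-visit mean, it says nothing about response on treatment.

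At stake is how a flat curve is read. Part B data up to the Part A database lock are summarized for regulatory submission (Part B SAP 4.9), and combined-period analyses may support submissions or publications (Part B SAP 4.1).

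**Working it through.** Part B has no power calculation and no stated durability figure, so there is nothing to reproduce. The check has four steps.

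1. **Is there a durability endpoint?** Protocol 4.3.4 and 7.4.2 and Part B SAP 4.4.1 name parameters and descriptive methods. None defines a Part B response, its maintenance, its loss or its duration. Part B SAP 4.1 mentions time-to-event data, but 4.4.1.1 lists no time-to-event endpoint. Part A SAP 4.5.1 does have related measures (share with a 1.5 g/dL Hgb rise by visit, time to first transfusion), and these are not carried over.

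2. **Illustration (all values assumed).** Twenty responders sit at +2.5 g/dL and 4 relapse to baseline.
   - The 4 withdraw, observed cases only: 16 × 2.5 / 16 = +2.5.
   - All 20 counted: (16 × 2.5 + 4 × 0) / 20 = +2.0. Maintained: 16 / 20 = 80%.
   - The 4 stay and transfusion holds them at +1.5: (16 × 2.5 + 4 × 1.5) / 20 = +2.3.
   - The 4 stay, but their post-transfusion values are deleted: 16 × 2.5 / 16 = +2.5, further from +2.0 than the +2.3.

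3. **Size over assumed ranges.** The reference is the mean in all patients without transfusion lift, and the terms are added as an approximation.
   - Dropout: share stopped × (mean of continuers − mean of stoppers). With 0–20% and a gap of 0–2 g/dL: 0 to 0.20 × 2 = +0.40 g/dL.
   - Transfusion: share recently transfused × lift. With 0–10% and 1–2 g/dL: 0 to 0.10 × 2 = +0.20 g/dL.
   - Off-drug values: −(share in the window × fall). With 0–5% and 1–3 g/dL: 0 to −0.05 × 3 = −0.15 g/dL.
   - Upward terms together: 0 to 0.40 + 0.20 = +0.60 g/dL.
   - If stoppers count as not maintained, an observed share of 70% becomes 70 × 0.95 = 66.5%, 70 × 0.90 = 63% or 70 × 0.80 = 56% with 5%, 10% or 20% stopped.

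   The illustration in step 2 uses a wider gap (2.5 g/dL) and a larger transfused share (20%) than these ranges. It shows the mechanism and is not a forecast.

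4. **Can off-drug values enter?** Part B windows run from −6 to +7 days around visits 14 days apart: 183–196, 197–210, 211–224, 225–238, 239–252 and so on. They leave no gaps, so a follow-up visit inside the summarized period always lands in one. For example, a last dose on Day 189 puts the visit on Day 189 + 63 = 252, inside 239–252.

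**The case against.** The strongest reply is that Part B is open-label, has a safety primary objective and tests nothing, and that the SAP does what Protocol 4.3.4 and 7.4.2 ask. Transfusion counts and units, hemolytic breakthrough (itself a loss-of-control event) and discontinuation by reason are all reported. Each by-visit table shows its number of observations, so attrition is visible. The stricter rules in Part A belong to its tested endpoints. Its bilirubin, LDH and exploratory by-visit summaries are also descriptive, and its de-facto estimand applies no intercurrent-event rule.

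Much of this stands. A reader might infer that durability is judged by observed-case means alone. The other planned summaries rule that out. A reader might also infer that durability will be overstated. The documents do not support that either: they give no stopping rate, transfusion rate or Hgb gap. The upward terms are zero if stopping and transfusion are rare, the dropout term is zero or negative if stoppers do as well as or better than continuers, and off-drug values pull the other way. Nor does Part B depart from a rule that Part A applied throughout.

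The reply does not supply the missing quantity. The extra summaries are separate aggregates. None is tied to whether a given responder remained one, and none changes how the Hgb and FACIT-F means are formed.

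**Conclusion.** The point holds as a gap in definition with a possible bias. The plan names durability of response as an objective and has no endpoint that measures it. The by-visit means may overstate maintained response, and they can mix on-treatment with off-drug values. The size cannot be computed from the documents. Under the assumed ranges it is 0 to +0.60 g/dL in mean Hgb from dropout and transfusion, less 0 to 0.15 g/dL in windows that receive off-drug values.

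No hypothesis test, type I error rate or Part A conclusion is affected. This is an inexpensive improvement that lets Part B answer its own question, not a flaw that invalidates it.

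**What to change.** Add to Part B SAP 4.4.1, descriptively and by Part A arm:

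- **(a) Maintained response at each 3-month landmark.** Hgb at least 1.5 g/dL above Part A baseline, with no transfusion and no non-permitted CAgD treatment since response was established. Discontinuation for any reason other than study closure counts as not maintained. Show a version limited to observed patients beside it, because counting every discontinuation as a loss is one defensible choice among several.
- **(b) Kaplan-Meier time to first loss of response among responders.** In the former BIVV009 arm the clock starts at Part A response (Week 26). Former-placebo patients first receive BIVV009 at Week 26, so theirs starts at first response in Part B. The SAP should say which visits establish that response.
- **(c) Clearer by-visit displays.** Flag post-transfusion values, and show follow-up values taken 9 weeks after the last dose apart from the on-treatment means.

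Do not simply set post-transfusion values to missing in the observed-case means. Part A pairs that rule with a mixed model. Here it would remove the failures and raise the mean, from +2.3 to +2.5 in the illustration.

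The inputs are already collected. Hematology, concomitant treatment and transfusions are recorded every 2 weeks (Protocol 6.1.5.1), with blood tests every 4 weeks under home infusion (Appendix K). The cost is SAP wording and a few tables, and the reported durability may be less favourable.
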